### 9.2.1.2. Radiographic (CT/MRI) Assessments

During the study, disease response will be assessed using CT scans with IV contrast of the neck (only if neck lymph nodes are involved, in which case full neck views must be obtained), chest, abdomen, and pelvis and any other location where disease was present at Screening. Subjects who are intolerant of IV CT contrast agents will have CT scans performed with oral contrast.

A separate CT scan and PET scan are preferred but, if the only available modality is combined/dual PET/CT scanner, then the CT portion of a PET/CT may be used in lieu of a dedicated CT.

Evaluation of other sites of disease by radiological imaging, physical examination, or other procedures as necessary (to be performed throughout the study using the same method of assessment used to assess disease at baseline), and review of hematology and clinical chemistry results may also occur at the site level.

Magnetic resonance imaging may be used to evaluate sites of disease that cannot be adequately imaged using CT (in cases where MRI is desirable, the MRI must be obtained at baseline and at all subsequent response evaluations). For all other sites of disease, MRI studies do not replace the required neck, chest, abdomen, and pelvic CT scans. Brain MRI and lumbar puncture are required only if clinically indicated.

### 9.2.1.3. Positron Emission Tomography (PET Scan)

FDG-PET is important for the complete assessment of response and progression in subjects with FL. Whole body FDG-PET scans (skull base to the proximal femur) should be done at screening, per investigator discretion. For subjects who are PET-positive at baseline, PET scans will be done at the time of maximal tumor reduction (eg, CR or 2 consecutive CT scans showing no further tumor reduction).

Assessment of PET results is based on published criteria (Juweid 2007). Visual assessment is considered adequate for determining whether a PET scan is positive, and use of the standardized uptake value is not necessary. A positive scan is defined as focal or diffuse FDG uptake above background in a location incompatible with normal anatomy or physiology, without a specific standardized uptake value cutoff. Other causes of false-positive scans should be ruled out. Exceptions include mild and diffusely increased FDG uptake at the site of moderate- or large-sized masses with an intensity that is lower than or equal to the mediastinal blood pool, hepatic or splenic nodules 1.5 cm with FDG uptake lower than the surrounding liver/spleen uptake, and diffusely increased bone marrow uptake within weeks after treatment.

#### **9.2.1.4. Bone Marrow Assessment**

An optional bone marrow biopsy, with or without aspirate, at Screening to document bone marrow involvement with lymphoma may be obtained at the investigator's discretion. A bone marrow biopsy obtained as routine standard of care may be used instead if taken up to 42 days before first dose of study drug. If bone marrow aspirate is obtained, determination of bone marrow involvement may be confirmed by flow cytometry. However, a bone marrow biopsy is required for documentation of a CR; a confirmatory bone marrow biopsy should be done preferably within 30 days of the initial documentation of CR. Bone marrow evaluation must include morphological examination and either flow cytometry or immunohistochemistry (IHC), if warranted, to confirm the presence or absence (complete remission) of lymphoma. If bone marrow involvement can be confirmed with morphology, IHC need not be done if this is not part of a study-site standard practice.

#### **9.2.1.5. Endoscopy**

CRs must be confirmed with endoscopy examination if the lymphoma originated from or involved the GI tract at diagnosis.

### **9.2.2. Endpoints**

#### **9.2.2.1. Primary Endpoint**

Overall response rate is defined as the proportion of subjects who achieve CR or PR.

#### **9.2.2.2. Major Secondary Endpoints**

Duration of response (DoR) will be duration from the date of the initial documentation of a response to the date of first documented evidence of PD (or relapse for subjects who experience CR). For those subjects who are still without progression/relapse, DoR will be censored at the last adequate tumor assessment.

PFS is defined as the duration from the date of the first daratumumab dose to the date of progression/relapse or death, whichever comes first. For those subjects who are still alive without progression/relapse, PFS will be censored at the last adequate tumor assessment.

Overall survival (OS) is defined as the duration from the date of the first daratumumab dose to the date of death. For those subjects who are still alive without progression/relapse, OS will be censored at the last date known to be alive.

Time to response is defined as the duration from the date of the first dose of daratumumab to the earliest date that a response (CR/PR) is first documented. For non-responders, it will be censored at the date of progressive disease/relapse or the date of the last adequate disease assessment, whichever comes first.

additional sampling is required. Procedures for sample collection, preparation, identification, storage, and shipment will be provided in the Laboratory Manual or equivalent document.

Additionally, blood samples should also be collected at the final visit from subjects who are discontinued from treatment. Subjects who discontinue treatment will also be asked to return for immunogenicity evaluation during the Follow-up Phase.

A blood sample should be drawn, if possible, for determination of antibodies to daratumumab any time an infusion reaction is observed or reported during the study. Daratumumab serum concentration will also be determined from the same infusion reaction sample for the purpose of interpreting immunogenicity data. These samples will be stored and evaluated if deemed necessary. If the infusion reaction results in treatment discontinuation, then subjects should undergo all scheduled safety and efficacy evaluations. Samples collected for the analysis of daratumumab immunogenicity/serum concentration may additionally be used to evaluate safety or efficacy aspects that address concerns arising during or after the study period or for the evaluation of relevant biomarkers by the sponsor or sponsor's designee.

#### **9.4. Biomarkers**

Biomarker analyses are dependent upon the availability of appropriate biomarker assays and may be deferred or not performed if, during or at the end of the study, it becomes clear that the analysis will have no scientific value, or if there are not enough samples or not enough responders to allow for adequate biomarker evaluation. In the event the study is terminated early or shows poor clinical efficacy, completion of biomarker assessments is based on justification and intended utility of the data. Samples for biomarker evaluations will be collected as specified in [Table 1](#).

##### **Determination of CD38 and CD59 Expression:**

During screening, subjects will be required to provide tumor samples for assessment of CD38 expression based on central testing using investigational IHC methodology under development (Section [9.1.2](#)). An additional fresh biopsy should be obtained whenever possible even if an archival sample is provided. Fresh tumor samples can be either lymph node excision or core needle biopsy; fine needle aspirates are not acceptable.

In addition to evaluating CD38 expression, fresh or archived biopsy samples may be evaluated in all subjects to identify markers predictive of response to daratumumab or prognostic markers for disease progression. Paraffin-embedded, formalin-fixed tumor tissue may also be subjected to DNA (eg, somatic mutations) and RNA analysis (eg, GEP, qRT-PCR, or RNA-seq) to determine if specific mutations or transcriptomic profiles (translocations, deletions, inversions, genes involved in B-cell signaling pathways, CD38 signaling pathways, or others) are associated with daratumumab response. Comparison of CD38 IHC results may be made to transcriptomic data. In addition to CD38, CD59 expression will be measured by IHC in a designated laboratory as an exploratory biomarker. CD59 is a complement inhibitory protein and can contribute to resistance to CDC, which may be important for daratumumab response.

A subject's study treatment should be discontinued if:

- The investigator believes that for safety reasons (eg, adverse event) it is in the best interest of the subject to discontinue study treatment
- The subject becomes pregnant
- The subject withdraws consent for administration of study treatment
- The subject initiates treatment with a prohibited medication
- The subject received concurrent (non-protocol) treatment for NHL
- The subject experiences unacceptable toxicity, including IRRs described in Section 6.3.3
- The subject's dose of daratumumab is held for more than 4 weeks (Cycle 1 to Cycle 6) or 6 weeks (Cycle 7 and beyond) should have study treatment discontinued, unless, after consultation with the sponsor and review of safety and efficacy, continuation is agreed upon
- The subject experiences disease progression (please see below). Relapse from CR is not considered as disease progression

A subject who experiences a second primary malignancy that cannot be treated by surgery alone must be withdrawn from the study. However, a subject who develops a malignancy that can be cured surgically may continue to receive the assigned study treatment and should continue to be followed for subsequent progression of lymphoma.

The primary reason for discontinuation of study treatment is to be recorded in the eCRF.

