### 9.1.4. Follow-up Phase

The Follow-up Phase will begin once a subject discontinues study treatment. Subjects who discontinue before disease progression (for other reasons such as an AE) must continue to have their regularly scheduled scans according to the [Table 1](#) until confirmed PD, death, the start of a new anticancer therapy, withdrawal of consent, lost to follow up, or the end of the study for that NHL subtype. After disease progression is documented, follow-up will occur at least every 16 weeks ( $\pm 2$  weeks). Subsequent anticancer therapy, second primary malignancies, and survival status will be recorded.

If the information is obtained via telephone contact, written documentation of the communication must be available for review in the source documents. If the subject has died, the date and cause of death will be collected and documented in the eCRF.

The end of the cohort for each NHL subtype is defined as 18 months after the last subject in the particular NHL subtype receives the first dose of daratumumab. After completion of an NHL subtype, the sponsor will ensure that subjects who are currently on treatment and receiving benefit, as determined by the investigator, will continue to receive daratumumab. The end of the study is defined as the completion of all three NHL subtypes.

not measurable but are thought to represent lymphoma. In addition, if more than 6 sites of disease are measurable, these other sites of measurable disease may be included as assessable disease.

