### **10.3. Withdrawal From the Study**

A subject will be withdrawn from the study for any of the following reasons:

- Lost to follow-up
- Withdrawal of consent for study participation
- Death
- The study investigator or sponsor, for any reason, stops the study or stops the subject's participation in the study

Before a subject is considered lost to follow-up, every reasonable effort must be made by the study-site personnel to contact the subject and determine the reason for discontinuation/withdrawal. The measures taken to follow up must be documented.

When a subject withdraws before completing the study, the reason for withdrawal is to be documented in the eCRF and in the source document. Study treatment assigned to the withdrawn subject may not be assigned to another subject. Subjects who withdraw will not be replaced. If a subject withdraws from the study, assessments outlined in the End-of-Treatment Visit should be obtained.

All adverse events, regardless of seriousness, severity, or presumed relationship to study treatment, must be recorded using medical terminology in the source document and the eCRF. Whenever possible, diagnoses should be given when signs and symptoms are due to a common etiology (eg, cough, runny nose, sneezing, sore throat, and head congestion should be reported as "upper respiratory infection"). Investigators must record in the eCRF their opinion concerning the relationship of the adverse event to study therapy. All measures required for adverse event management must be recorded in the source document and reported according to sponsor instructions.

The sponsor assumes responsibility for appropriate reporting of adverse events to the regulatory authorities. The sponsor will also report to the investigator (and the head of the investigational institute where required) all serious adverse events that are unlisted (unexpected) and associated with the use of the study drug. The investigator (or sponsor where required) must report these events to the appropriate Independent Ethics Committee/Institutional Review Board (IEC/IRB) that approved the protocol unless otherwise required and documented by the IEC/IRB.

Subjects (or their designees, if appropriate) will be provided with a "wallet (study) card" and instructed to carry this card with them for the duration of the study indicating the following:

- Study number
- Statement, in the local language(s), that the subject is participating in a clinical study

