The Follow-up Phase will begin once a subject discontinues study drug, and will continue until death, loss to follow up, consent withdrawal for study participation, or end of study, whichever occurs first.

The end of the cohort for each NHL subtype is defined as 18 months after the last subject in the particular NHL subtype receives the first dose of daratumumab. After each NHL subtype

completes the study, the sponsor will ensure that subjects, who are currently on treatment and receiving benefit, as determined by the investigator, will continue to receive daratumumab. The end of the study is defined as the completion of all three NHL subtypes.

Throughout the Treatment Phase and Follow-up Phases, assessment of tumor response and disease progression will be conducted by investigators in accordance with the Cheson 2014¹ response criteria. Identical methodology should be used for disease assessment at screening and throughout the course of the study. Radiological and PET scans should be performed and collected according to instructions from the independent imaging laboratory. A central review of the response assessments may be performed if deemed necessary.

Safety evaluations will include AE monitoring, physical examinations, electrocardiogram (ECG) monitoring, clinical laboratory parameters (hematology and chemistry), vital sign measurements, and Eastern Cooperative Oncology Group (ECOG) performance status. Measures to prevent infusion-related reactions will include preinfusion medication with methylprednisolone, acetaminophen (or paracetamol), and an antihistamine before each daratumumab infusion.

Blood samples will be drawn for assessment of serum concentration (pharmacokinetics) of daratumumab and the generation of antibodies to daratumumab (immunogenicity) from all subjects according to the Time and Events Schedule. In addition, biomarker samples will be collected to identify markers predictive of response (or resistance) to daratumumab.

The primary efficacy endpoint, is Overall Response Rate (ORR) defined as the proportion of subjects who achieve CR or PR.

Major secondary efficacy endpoints are duration of response (DoR), PFS, overall survival (OS), and time to response (TTR).

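### Protocol 10.2 can be read as ending survival follow-up after a second primary malignancy; one phrase should be reworded, though the possible effect on OS is small

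*Protocol*

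**What the plan says.** Protocol 10.2 first lists reasons to stop daratumumab, under the lead-in "A subject's study treatment should be discontinued if". The rule at issue follows: "A subject who experiences a second primary malignancy that cannot be treated by surgery alone must be withdrawn from the study". The next sentence lets a subject whose new malignancy is surgically curable stay on treatment and be followed for lymphoma progression. The section then closes with "The primary reason for discontinuation of study treatment is to be recorded in the eCRF".

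Leaving the study is handled separately in Protocol 10.3, which begins "A subject will be withdrawn from the study for any of the following reasons". It names loss to follow-up, withdrawal of consent, death, and a decision by the investigator or sponsor. Second malignancy is not named.

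On follow-up, Protocol 9.1.4 says "The Follow-up Phase will begin once a subject discontinues study treatment". It also lists second primary malignancies and survival status among the items recorded after progression. SAP 1.1 says the Follow-up Phase "will continue until death, loss to follow up, consent withdrawal for study participation, or end of study, whichever occurs first".

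On OS censoring, Protocol 9.2.2.2 says "For those subjects who are still alive without progression/relapse, OS will be censored at the last date known to be alive". SAP 4.3.2 likewise censors subjects alive at the cut-off at the date last known alive.

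**The concern.** The protocol distinguishes stopping treatment from leaving the study, and this rule uses the second term, with mandatory wording. A site that follows it literally would collect no survival data after the second malignancy. OS would then be censored at an event that probably worsens prognosis, so the censoring is informative and the Kaplan-Meier curve is pushed upwards. If the authors meant only that daratumumab should stop, the wording does not say so, and survival data could be lost for no stated reason.

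**Working it through.** **1. The texts side by side**

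| Place | What it implies for these subjects |
|---|---|
| Protocol 10.2, the rule | Leaves the study, if read literally |
| Protocol 10.2, next sentence | Surgically curable cases go on being followed; by contrast the others might not be |
| Protocol 10.2, list before and sentence after | Both concern stopping treatment, which supports a treatment-only reading |
| Protocol 10.3 | Second malignancy is not a named reason; only the investigator/sponsor item could cover it |
| Protocol 9.1.4 | Stopping treatment opens follow-up |
| SAP 1.1 | Follow-up ends for four reasons; second malignancy is not one |

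Both readings are available. The literal one conflicts with 9.1.4 and SAP 1.1 by implication only, because neither mentions these subjects.

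**2. Inputs for the size**

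The plan states no figure to reproduce. From the documents: each cohort ends 18 months after its last subject's first dose; cohorts are 100 (MCL) and 55 (DLBCL, FL) at full enrolment, and 20, 15 and 15 in Stage 1. Assumed: a proportion p of 1 to 5% affected by month 18; death hazard multiplied by k = 2 to 5 after onset; median OS without a second malignancy of 12 or 24 months; constant hazards.

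Expected affected subjects (n × p): 1 to 5 of 100; 0.55 to 2.75 of 55; 0.2 to 1 of 20; 0.15 to 0.75 of 15.

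**3. Upper bound: the rule acts for all 18 months and no later survival data are obtained**

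Let h = ln 2 / median OS and L = hazard of second malignancy.

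- True OS: S = exp(−18(h+L)) + L·[exp(−18kh) − exp(−18(h+L))] / (h + L − kh)
- Kaplan-Meier limit when censored at onset: exp(−18h) = 35.4% (median 12) or 59.5% (median 24)
- L from crude incidence: L/(h+L)·[1 − exp(−18(h+L))] = p
- L from net risk: L = −ln(1−p)/18

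Worked case (median 12, p = 5% crude, k = 5): h = 0.0578 and L = 0.0046, so S = 33.2%. The overstatement is 35.4 − 33.2, or 2.17 points before rounding.

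| Median OS | p, k | Overstatement, crude (points) | Overstatement, net (points) |
|---|---|---|---|
| 12 | 1%, 2 | 0.22 | 0.13 |
| 12 | 2%, 3 | 0.66 | 0.41 |
| 12 | 5%, 5 | 2.17 | 1.36 |
| 24 | 1%, 2 | 0.17 | 0.13 |
| 24 | 2%, 3 | 0.58 | 0.45 |
| 24 | 5%, 5 | 2.22 | 1.73 |

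**4. Narrower case: the rule acts only while subjects are on treatment**

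The total treatment-exit hazard, death included, is set to ln 2 / (2, 4 or 6 months). Second malignancies after treatment are followed as usual. The lowest result is 0.04 points (median OS 24, 2 months on treatment, 1% net, k = 2; 0.16% affected). The highest is 1.44 points (median OS 12, 6 months on treatment, 5% crude, k = 5; 34.6% against 33.2%, 3.4% affected).

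**5. Against sampling error**, SE = √(S(1−S)/n) at the Kaplan-Meier limit

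- n = 100: SE 4.8 to 4.9 points. Upper bound 2.17/4.78 = 0.45; on-treatment case 1.44/4.76 = 0.30.
- n = 20: SE 10.7 to 11.0 points; 2.17/10.69 = 0.20.
- n = 15: SE 12.3 to 12.7 points; 2.17/12.34 = 0.18.

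**6. Cross-check by simulation** (200,000 subjects per scenario, net risk 1 to 5%, follow-up 18 to 36 months)

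With the death hazard unchanged after onset, the shift is essentially zero. At twice the hazard, 12-month OS rises by about 0.1 to 0.5 points; at five times, by about 0.2 to 1.1. The worst median shifts are 11.6 to 11.9 months and 22.6 to 24.1 months.

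**The case against.** The treatment-only reading is well supported. The amendment summary names 10.2 as the section on discontinuing study treatment; the sentences around the rule concern treatment; 10.3 omits second malignancy; and 9.1.4 treats second malignancy as something to record. Section 10.2 is also only partly visible, and Table 1 is not visible at all, so unseen text may settle the matter. All this stands, and it is why the point concerns ambiguous wording and not an established contradiction. It does not remove the case for the edit: the rule still names the study and not the treatment, and the contrast with surgically curable cases leans the other way.

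It is also fair that every input to the size is assumed, that the largest figures pair the highest rate with the highest hazard, and that Stage 2 is optional, so Stage 1 sizes may be all there is. Deaths might also be captured through follow-up of unresolved serious adverse events (Protocol 12.3.2), which would shrink the effect further.

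A reader might infer that OS censoring is undefined for these subjects. It is not: last date known alive covers them under both documents. The issue is only that, under the literal reading, the second malignancy would fix that date.

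**Conclusion.** The point holds as a low-severity wording correction. If the rule is applied literally, OS is censored informatively and 18-month OS is overstated by roughly 0.1 to 2.2 points, or 0.04 to 1.4 if the rule acts only during treatment. That is at most 0.45 of a standard error at n = 100 and about 0.2 at Stage 1 sizes, given the assumed rates, hazard ratios and medians.

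A reader might infer a demonstrated OS bias in favour of daratumumab. The documents do not support that: they allow the treatment-only reading, give no rate of second malignancy, and do not show how sites apply the rule. The futility rules and the powering rest on ORR. The SAP summarises OS by Kaplan-Meier with no null hypothesis. The protocol's visible text also mentions comparing OS above and below the CD38 threshold; the effect on that secondary comparison was not quantified.

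**What to change.** In Protocol 10.2, replace the requirement to leave the study with: *must be discontinued from study treatment; survival follow-up continues per Section 9.1.4 unless consent is withdrawn*. Daratumumab still stops, scans still end at the points 9.1.4 already sets, and sample size, alpha and power do not change.

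The cost is one phrase and a few survival contacts for the few subjects affected (1 to 5 of 100 under the assumptions). At a 16-week interval that is at most about 5 contacts each over 18 months (78/16 = 4.9), and fewer with later onset or earlier death.

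No change to 9.1.4 is proposed. Its visible text says "After disease progression is documented, follow-up will occur at least every 16 weeks", which leaves open the contact interval for subjects who start new therapy before progression. That is a wider question, reaching subjects with no second malignancy, and Table 1 may already answer it.
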